Cover page

Title of study

Maternal role in sensory motor stimulation for Oral Feed Establishment in preterm neonates: MSMS trial

NCT number

NCT05484726

Date of document

21 April 2024

Maternal role in sensory motor stimulation for Oral Feed Establishment in preterm neonates: MSMS trial

Oral feed establishment is one of the most challenging milestones for preterm neonates. It is becoming an emerging challenge for neonatologists with an improvement in the survival of preterm neonates. A successful transition from full gavage (tube) feeding to independent oral feeding is considered an important milestone of neonatal neurodevelopment maturation. It has been estimated that about 40% of preterm neonates face difficulty transitioning from gavage to oral feeding (1).

Tube feeding-related problems are commonly observed in neonates. A literature review regarding the safety profile of having a feeding tube shows that it is not risk-free. Major problems enlisted are mechanical, functional, nutritional, biological and neurodevelopmental (mental motor delay) (2-5).

According to Heidelise Als' "Synactive Theory" in growing fetus and neonate, developmental maturation is done by integrating neonatal internal physiological status and functional demands with multisensory inputs from the environment (6,7). In preterm neonates, synergistic effects of combined oral and non-oral sensorimotor (tactile/kinesthetic) interventions have shown promising results (8). It helps augment their experience to exercise their innate (sucking) reflex that ultimately decreases transition time from introduction to safe full independent oral feeding (9). Feeders and grower neonates are ideal for oral stimulation for oral feed establishment.

The ideal time to start oral feeding in preterm neonates is still debatable. In developing fetus shows sucking, swallowing and breathing at 15, 14 and 10 weeks of gestation, respectively (10). Feeding development undergoes maturational processes throughout gestation, from non-coordinated sucking and swallowing movements to fully coordinated suck-swallow-breathe, usually occurring after 34 weeks. Unlike the term sucking reflex, preterm neonates have a predominant expression pattern of sucking with no suction. Lau et al. demonstrated that around 30 weeks of post-menstrual age (PMA), healthy preterm neonates could complete their successful oral feeding within 20 minutes using an immature sucking reflex (11).

Family-centred care (FCC) is, in fact, developmentally supportive care that helps develop bonding (12). Intermittent kangaroo mother, as a part of FCC, benefits from maternal-neonatal bonding (13). Similarly, the role of maternal involvement in pre-feeding sensorimotor stimulation is a hidden corner in research. To our knowledge, not even a single international or national study is available in this regard.

In resource-constrained setups with limited properly trained speech therapists and neonatal nurses, mothers can be involved in pre-feeding sensory motor stimulation after training and teaching to improve their feeding performance. Within this context, the current study aims to determine the following: 1) the maternal role in sensory-motor stimulation for oral feed establishment in preterm neonates, 2) determine the effect of sensory-motor stimulation offered by the mother on the onset of oral feeding, and 3) the efficiency of mother-mediated stimulation techniques on oral feeding compared to trained nurses.

Keywords

Prematurity sensory-motor stimulation oral feed establishment, feeding intervention

Material and methods

An interventional, prospective, randomized control trial was conducted after ethical approval from the Institutional Review Board of Fatima Memorial Hospital (FMH-07-2021-IRB-929-M). The authors confirm that this intervention's ongoing and related trials are registered in the ClinicalTrials.gov platform—accession number NCT05484726. The study protocol can be accessed at <https://www.clinicaltrials.gov/ct2/show/NCT05484726>.

Study hypothesised that preterm babies who receive sensory motor stimulation from their mothers as compared to trained nurses, are

- Start taking oral feed at the same time as compared to the control group
- Take the same amount of milk at the commencement of oral feeding
- Take milk with equal efficiency
- Not face more adverse effects

The study period spans 16 months, from March 2022 to July 2023, in the department of Neonatology, Fatima Memorial Hospital, Lahore. We enrolled all preterm neonates of gestation age 28 to 34 weeks who were admitted to NICU during the study period after seeking consent from parents or guardians. All these neonates were haemodynamically stable, established gavage feed, had no respiratory distress, no need for respiratory support except LFNC and did not receive any kind of analgesics at time of enrollment.

However, all those neonates having major anomalies incompatible with life, major malformations, syndromic babies, cleft lip and palate, genetic disorders, haemodynamically unstable babies including IVH (grade III & IV), haemodynamically significant PDA (HsPDA) requiring antifailure therapy, NEC (stage II & III) or anemia requiring blood transfusion. All those neonates with adverse events including cough with choking, breath holding, choking, aspiration, tachycardia HR > 200/min, bradycardia HR < 100/min, apnea > 15 sec, tachypnea RR > 70/min while stimulation or feeding were excluded.

Protocol

Interventional Study Model: Factorial Assignment

- Maternal involvement in perioral sensory-motor stimulation be in three stages
 - Observer status
 - Performing under supervision
 - Independent
- Intervention period: 5 days as
 - Training phase (T): T1 and T2 (for mothers by the nurse)
 - Direct feeding phase (D): F1, 2, and 3 (oral feed was offered to neonate)
- Stimulation for 7 minutes and 15 minutes before feeding twice a day at 1100 and 1700 hrs.
- Two groups
 - Intervention group (G I): by mothers
 - Control group (G II): by staff nurses

Number of Arms: 2

Masking: Single (Care Provider)

The mothers, medical staff involved in general care, nursing staff involved in the intervention, and doctors conducting the assessment of oral feeding skills (OFS) were all blinded to allocation. The nursing staff was informed at the time of intervention that participating infants received either sensory motor stimulation or sham oral stimulation depending on group allocation.

Allocation

Randomization was done using a random Alloc Software environment. Gestation age-based stratification was done using 3 blocks design of 28 to 30, 30+1 to 32 & 32+1 to 34. Random allocation of neonates into the intervention or control groups by stratum using lottery method.

Blinding

The mothers, medical staff involved in general care, nursing staff involved in intervention and doctors conducting the assessment of oral feeding skills (OFS) were all blinded to allocation. The nursing staff was informed at the time of intervention that participating infants received either sensory motor stimulation or sham oral stimulation depending on group allocation.

Sample size

The sample size was 46 (23 each in interventional and control groups) and calculated with a 95% confidence level, 10% margin of error and 5% level of significance by taking feeding-related problems as 40%. It was done by using openepi.com.

Initially only 46 neonates were enrolled in study. But later an immense maternal response was observed. Mothers were ready to learn and involve in sensory motor stimulation of their neonates. Hence, the final total study population size was 97 with 49 in experimental and 48 in control group.

Procedure of intervention

- The study intermediation was started not before 30 weeks of postmenstrual age when full gavage feeding was established with the addition of supplements.
- All mothers in this study was involved in gavage feeding before involvement in the procedure.
- Trained nurses taught details of sensory-motor stimulation to mothers in easily understandable languages (annexure 1 in (a) English and (b) Urdu). This procedure has been adapted from modified from PIOMI and Fucile (14,15).
- Stimulation was done for 7 minutes and at least 15 minutes before feeding twice daily at 1100 and 1700 hrs till full oral feed establishment (expected time 28 days chronological age)
- Oral feeding was offered using a bottle with a slow-flow nipple.
- Time monitoring for feeding was strictly followed
- Infants was fed for a maximum of 20 min, and feeding was discontinued early if adverse events occur.

Arms and intervention

- Study groups for sensory motor stimulation (5 minutes) + pacifier (2 minutes)
 - Intervention group (G1) : by mothers
 - Control group (G 2) : by staff nurses

Experimental: Intervention group (Group 1)

- Maternal involvement was done in three stages for the intervention group as
 - Observer status
 - T1: Nurses performing all steps while mother observer status
 - T2: Nurses perform all steps in front of the mother and a pacifier was offered by the mother
 - Performing under supervision
 - D1: Mother performs all steps and oral milk was offered by the nurse while the mother observes.
 - D2: Mother performing all steps and offering oral milk while the nurse is supervising

- Independent
 - D3: Mother performing all steps independently
- Study groups for sensory motor stimulation
 - Assigned intervention perioral sensory motor stimulation Step 1 - 6 over 5 minutes + pacifier 2 minutes for total duration of 7 minutes.
 - Step 1: With the help of the index finger, on the external surface of the cheek, make a circle starting from the angle of the mouth towards the ear then back 7x each cheek
 - Step 2: While holding both sides of the cheek with help of the thumb and index finger repeat step 1 7x each cheek
 - Step 3: Move index finger from one corner to opposite one over both lips separately 7x each lip
 - Step 4: Gentle massage and compress the gums from center to back of mouth 7x each half of the gum
 - Step 5: Move the finger from front to back on the hard palate while applying gentle pressure 7x
 - Step 6: Displace the center of the tongue with gentle pressure 7x
 - Offer pacifier at the end 2 minutes Note: 7x means 7 times

Control group / Sham Comparator (Group II)

All steps were same as intervention group and was performed by trained staff nurses

Data Collection

All relevant maternal and neonatal data (baseline measures) were collected on a specially designed proforma.

Baseline measures

- Maternal demographic and clinical data include
 - Age in years
 - Gravidity / number of pregnancies measured in numbers as primigravida (PG), 2-3 or ≥ 4)
 - Educational qualification as uneducated, primary, secondary or higher
 - Previous preterm baby measured as yes or no
 - Job status as working-lady or home-maker
 - Diabetes mellitus, hypertensive disorders and anemia as yes or no
- Neonatal demographic data includes
 - Gender as male or female
 - Gestation age measured in weeks
 - Mode of delivery as spontaneous vaginal delivery (SVD) or low segment caesarian section (LSCS)
 - Birth weight measured in kg
 - Weight for gestation age. It can be appropriate for gestation age (AGA), small for gestation age (SGA) or large for gestation age (LGA)
 - Place of birth as inborn or out-born
 - Neonates with respiratory failure may need respiratory support that was measured as
 - Requirement of invasive mechanical ventilation (IMV) along with duration in days as median with IQR

- Non invasive ventilation (NIV) along with duration in days as median with IQR
- Oxygen as low flow nasal cannula (LFNC) along with duration in days as median with IQR
- Neonates with prophylactic caffeine therapy given to all neonates < 32 weeks of gestation age
- Respiratory distress syndrome (RDS) was diagnosed on clinical and radiological features of reticulo-nodular shadowing
- Apnea was diagnosed on basis of breath holding spells for > 20 second
- Hemodynamically significant patent ductus arteriosus (HsPDA) diagnosed by echocardiography
- Necrotizing enterocolitis (NEC) diagnosed using modified Bell's scoring (stage 1)
- Feeding intolerance diagnosed as aspirates > 20% of previous feed ± abdominal distension of > 2cm from base line
- Sepsis (leukocytosis or leukopenia or ANC<150 along with raised CRP and platelets <100 and or positive blood culture)
- Seizures
- Discharge weight in kg
- Duration of stay in NICU in days
- Neonatal feeding characteristics at time of enrollment in study include
 - Postmenstrual age (PMA) measured in weeks
 - Chronological age (ChA) measured in weeks
 - Time/duration to achieve full gavage/tube feed measured in days
 - Daily milk intake (ml/kg/day) when sensory motor stimulation was started
 - Volume of feed prescribed for each feed (ml)

The **outcome** measured were documented daily twice a day (11.00 and 17.00 hrs) until achievement of full oral feed. Full oral feed was volume of 120-140ml/kg/day taken orally. However, to make calculations concise, for both groups, all outcome parameters were documented on proforma for fixed time (11.00 am) for D1, D2, D3, D5, D7 and D14.

- Primary Outcome Measure
 - Transition time to full oral feeding is the time interval between commencement of perioral sensory stimulation on D1 to establishment of full oral feed in both groups. It was done daily till 14th day of perioral sensory motor stimulation. Transition time to full oral feeding was the day at which baby was able to take oral feed of volume of 120-140ml/kg/day.
 - Improvement (change) in efficiency oral feed establishment in terms of amount and time. It was classified into four levels depending upon the level of maturity in ascending order as follows:
 - Level 1: PRO < 30% and RT < 1.5 ml/min
 - Level 2: PRO < 30% and RT ≥ 1.5 ml/min
 - Level 3: PRO ≥ 30% and RT < 1.5 ml/min
 - Level 4: PRO ≥ 30% and RT ≥ 1.5 ml/min

For our RCT, efficacy was measured as the achievement of L4 for the intervention group vs the control group.

- Adverse outcome monitoring was done for every neonate from first day of enrollment in study (D1) till establishment of full oral feed (by D14 expected). These include non-life threatening adverse events including cough, tachycardia HR 180-200/min, bradycardia HR120 - 100/min, , tachypnea RR 60 - 70/min while maintaining SpO2 of >90% at room air
- Secondary Outcome Measure:
 - Total volume (TV) taken during each feed
 - Volume taken during the first 5 min (TV₅) out of total feed taken orally
 - Rate of transfer (RT) ml/min i.e., how long it neonate takes to finish oral feed.
 - Overall transfer (OT percent) volume taken/total volume prescribed. It shows trend towards oral feed establishment.
 - Proficiency (PRO percent) volume taken during the first 5 min/total volume prescribed.
 - SSB (Suck Swallow Breaths) coordination coordinated, developed pattern of suck swallow and breathe. It is a subjective assessment.

Statistical analysis

The statistical software IBM SPSS Statistics version 21 (SPSS, Chicago, IL) was used for the statistical analysis of the data. Appropriate bivariate analysis was performed to identify the unadjusted differences between the cases and controls. Categorical variables were expressed as frequencies and percentages. According to Shapiro Wilk test all continuous variables were asymmetrically distributed. Mann–Whitney U test was used for nonparametric continuous variables and were described as medians and inter quartile range (IQR). Fisher exact/Chi square test was used to compare categorical variables. Mann-Whitney test was used to compare continuous variables. The p-value of < 0.05 was taken as statistically significant.

Results

During the research period, 1009 newborns were admitted to the Neonatal Intensive Care Unit (NICU). Among them, 142 were born prematurely, with gestational ages falling between 28 and 34 weeks. Out of the preterm neonates, a total of 130 were eligible for the study, as 12 had to be excluded for various reasons. These exclusions included 2 cases where mothers experienced serious postnatal complications, 1 instance of parental refusal to participate, 1 case with incomplete data, and 8 cases that did not meet the inclusion criteria due to different reasons such as syndromic features, cleft lip and palate, suspected inborn error of metabolism (IEM), intraventricular hemorrhage (grade IV), and hemodynamically significant patent ductus arteriosus (HsPDA). Consequently, 130 neonates were included in the study and randomly assigned, with 65 in each group for intervention and control. Sensory motor stimulation (SMS) was administered to 107 of these neonates, and the study was completed with 97 neonates (as illustrated in Figure 1).

The sociodemographic and clinical characteristics of both mothers and neonates are shown in Table 1. There were no statistically significant differences between groups regarding maternal age, gravidity, education, previous preterm neonates, job status and pregnancy related issues (hypertensive disorder of pregnancy, gestational diabetes, and anemia). Similarly, neonatal characteristics regarding gender, mode of delivery, gestation age, birth weight, weight for gestation age, place of delivery, need and duration of invasive mechanical ventilation (IMV), non

invasive ventilation (NIV) and low flow nasal cannula (LFNC), apnea, RDS, use of caffeine, HsPDA, NEC stage 1, feed intolerance, sepsis, and seizures. (Table 1).

There was also no significant difference in feeding characteristics. The feeding characteristics assessed were postmenstrual (PMA), chronological (ChA) age, and weight at enrollment, time to full gavage feed establishment, amount of milk feed advised for each feed and day on D1, D2, D3, D5, D7 and D14. (Table 2).

Table 3 provides an overview of both the primary and secondary outcomes observed in both study groups. When examining the primary outcome measures, there were no significant differences observed in terms of the time it took to establish full oral feeding, adverse events, or the effectiveness observed during oral assessments. The findings indicate that neonates in the experimental group demonstrated oral feeding skills that were comparable to those in the control group. These skills were measured in terms of volume (both total and during the initial 5 minutes of feeding), feeding rate, overall transfer, proficiency, and the coordination of suck, swallow, and breath (Table 3).

References:

1. da Rosa Pereira K, Levy DS, Procianoy RS, Silveira RC. Impact of a pre-feeding oral stimulation program on first feed attempt in preterm infants: Double-blind controlled clinical trial. *PLoS One*. 2020 Sep 9;15(9):e0237915. doi: 10.1371/journal.pone.0237915. PMID: 32903261; PMCID: PMC7480839.

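### The hypotheses claim sameness and no more adverse effects, but the analysis only tests for a difference, with no margin or confidence interval, so calling feeding skills comparable rests on non-significance

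*Combined protocol and SAP*

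**What the plan says.** The study hypotheses (Material and methods) compare stimulation by mothers with stimulation by trained nurses. Three state sameness. On timing, the maternal arm is to "Start taking oral feed at the same time as compared to the control group". The second hypothesis concerns volume, where infants are expected to "Take the same amount of milk at the commencement of oral feeding". A third, on feeding performance, is that they "Take milk with equal efficiency". The fourth is of the non-inferiority type: "Not face more adverse effects".

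Under Primary Outcome Measure, "efficacy was measured as the achievement of L4 for the intervention group vs the control group". Transition time to full oral feeding and adverse outcome monitoring stand in the same list.

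The Statistical analysis section says its purpose is to find unadjusted differences. Continuous variables are compared by Mann-Whitney, and "Fisher exact/Chi square test was used to compare categorical variables". The decision rule is "The p-value of < 0.05 was taken as statistically significant". No margin and no confidence interval for a between-arm difference appear anywhere.

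The Results report no significant differences in time to full oral feeding, adverse events or efficacy. They then say that the findings indicate *comparable* feeding skills in volume, rate, overall transfer, proficiency and suck-swallow-breathe (SSB) coordination. Table 3 gives medians or counts and p-values only.

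**The concern.** A test of no difference controls the risk of declaring a difference that is not there. For these hypotheses the costly error is the reverse: treating mothers' delivery as the same as nurses' when it is worse. A rule of p ≥ 0.05 does not control that error, and small numbers make it more likely.

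This is the trial's central question, since the stated rationale is that trained mothers could do this work where trained staff are scarce. For time, L4 and adverse events, reporting no significant difference is accurate as worded, but it leaves the sameness and not-more hypotheses unanswered. For the feeding skills, *comparable* goes further than the tests allow.

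**Working it through.** **Is there a margin?** The Sample size section gives 95% confidence, a 10% margin of error and a 40% rate of feeding problems. These are inputs to the precision of one proportion, n = z²p(1-p)/d² = 1.96² × 0.40 × 0.60 / 0.10² = 92.2. They name no between-arm difference and no power. (That the formula does not give the stated 46 is a separate matter.)

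**The printed p-values.** Table 3 percentages run across the arms (35 of 71 = 49.3%), so within-arm rates must be rebuilt from the counts over 49 and 48. One-sided Fisher tests in the observed direction reproduce the L4 p-values (0.331, 0.528, 0.434) and the adverse-event p-values (0.234, 0.563, 0.570, 0.253). The two-sided values are 0.623, 1.0, 0.819 and 0.385, 1.0, 1.0, 0.495. All are non-significant either way.

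**Binary outcomes.** Newcombe 95% CI, with d = p₁ - p₂ and Wilson limits (l, u) for each arm:

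- lower = d - √[(p₁ - l₁)² + (u₂ - p₂)²]
- upper = d + √[(u₁ - p₁)² + (p₂ - l₂)²]

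Example, L4 at D14: p₁ = 35/49 = 0.714 (0.576, 0.822) and p₂ = 36/48 = 0.750 (0.612, 0.851). Lower = -0.036 - √(0.138² + 0.101²) = -0.207. Upper = -0.036 + √(0.108² + 0.138²) = +0.139.

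| Outcome | Mothers /49 | Nurses /48 | Difference, points (95% CI) |
|---|---|---|---|
| L4, D5 | 12 | 9 | +5.7 (-10.7 to +21.8) |
| L4, D7 | 16 | 15 | +1.4 (-16.7 to +19.4) |
| L4, D14 | 35 | 36 | -3.6 (-20.7 to +13.9) |
| Adverse events, D1 | 36 | 31 | +8.9 (-9.3 to +26.4) |
| Adverse events, D2 | 14 | 14 | -0.6 (-18.2 to +17.0) |
| Adverse events, D3 | 12 | 12 | -0.5 (-17.5 to +16.4) |
| Adverse events, D5 | 2 | 0 | +4.1 (-3.9 to +13.7) |
| SSB, D1 | 23 | 22 | +1.1 (-18.1 to +20.2) |
| SSB, D2 | 33 | 27 | +11.1 (-8.0 to +29.2) |
| SSB, D3 | 33 | 32 | +0.7 (-17.5 to +18.9) |
| SSB, D5 | 40 | 37 | +4.5 (-11.6 to +20.5) |
| SSB, D7 | 39 | 36 | +4.6 (-12.0 to +21.0) |

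The intervals are 32 to 38 points wide, except adverse events at D5 (18). Rows with 0% or 100% in both arms are tighter, about -7 to +7.

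**What the decision rule would have passed.** Hold the nurses' arm as observed:

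- L4 at D14 of 29/49 vs 36/48, 15.8 points lower: two-sided Fisher 0.131, one-sided 0.075, chi-square 0.098.
- D1 adverse events of 39/49 vs 31/48, 15.0 points higher: 0.117, 0.077 and 0.099.

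Both would be reported as no significant difference.

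**Time to full oral feed** (10 (7–13) vs 9 (7–13) days, p = 0.531). The documents give no SD. The quartiles suggest about 6/1.35 = 4.4, so I assume 3.5, 4.45 and 5.5. SE = SD × √(1/49 + 1/48) / √0.955, where 0.955 is the efficiency of Mann-Whitney under normality, giving 0.73, 0.92 and 1.14. The z for p = 0.531 is 0.626, so the shift is 0.46, 0.58 or 0.72 days, with direction taken from the medians. Shift ± 1.96 SE gives -1.0 to +1.9, -1.2 to +2.4 or -1.5 to +3.0 days. Integer data sets rebuilt to the printed quartiles, with a Mann-Whitney p near the printed one, gave Hodges-Lehmann intervals mostly of -1 to +2 days, some -1 to +3.

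**Volume, RT, OT and PRO** (30 rows). Take the chance that a maternal-arm infant scores above a nurse-arm infant (0.5 = no difference). SE = √[98/(12 × 49 × 48)] = 0.0589, so the half-width is 0.115, or 0.108 if half the values are tied. For D1 volume (p = 0.803) the deviation is about 0.015, which leaves about 0.40 to 0.63, or the mirror image 0.37 to 0.60, since equal medians do not show the direction.

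**The case against.** The best defence is that the challenged inference is one word, *comparable*, applied to secondary outcomes. The Results do not claim equivalence or non-inferiority, the wording on the primary outcomes is accurate, many point estimates are close, and some favour mothers. That is fair and rules out any charge that a deficit was hidden. It does not help the hypotheses, which claim sameness and which nothing in the analysis can answer.

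It can also be said that intervals alone will not settle every hypothesis. This stands:

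- No listed outcome measures the start of oral feeding. Transition time is only the nearest one.
- The adverse-event rows count non-life-threatening events, and infants with the more serious events during stimulation or feeding were excluded.
- Outcome recording ran to day 14. If some infants had not reached full oral feed by then, their coding affects the time interval.
- The printed SSB p-value at D3 (0.746) does not match its counts (one-sided Fisher 0.557, two-sided 1.0, chi-square 0.943), so that interval depends on an unresolved entry.

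These are further limits on what can be claimed. They do not rescue an inference from non-significance. Intervals for the whole of Table 3 are bulky, so rows tied to the hypotheses should come first.

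**Conclusion.** The concern holds. The analysis cannot support sameness or the not-more hypothesis, and *comparable* rests on similar point values and non-significance. Among completers, the data leave open an L4 rate at D14 about 21 points lower with mothers, or a D1 adverse-event rate about 26 points higher, as well as differences in mothers' favour. For time to full oral feed, a delay of about 2 to 3 days is not excluded.

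The binary intervals need only the Table 3 counts and the denominators 49 and 48. The time and rank-based intervals are approximations, resting on an assumed SD and on reported p-values. All of them ignore attrition: "130 neonates were included in the study and randomly assigned, with 65 in each group for intervention and control", yet 97 were analysed, so 65 - 49 = 16 and 65 - 48 = 17 infants per arm (33 in all) are missing. The documents give no margin, so I do not judge which of these differences would matter clinically.

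**What to change.** This should be corrected before the conclusions are relied on.

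1. Report risk differences with two-sided 95% CIs for L4, adverse events and SSB, by Newcombe or another method that handles zero cells.
2. Report Hodges-Lehmann differences with 95% CIs from the raw data for time to full oral feed and for the volume, RT, OT and PRO rows. These replace the approximations above. State how any infant not at full oral feed by day 14 was coded.
3. State that equivalence and non-inferiority were not formally tested, and that the intervals cover 97 completers of 130 randomised. Note that the start of oral feeding was not measured and that the adverse-event rows cover only the milder events.
4. Replace *comparable* with wording such as: no difference detected; the data do not exclude differences as large as the interval limits.
5. Label any comparison with a margin post hoc and exploratory, since the results are known.

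The cost is one interval for each of the 46 rows of Table 3 (time 1, adverse events 5, L4 4, and six rows for each of six other measures) and a few sentences in the analysis and results sections. All of it comes from data in hand. The price is a longer table and a less favourable conclusion.

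### Neonates are allocated singly with no sibling rule although the mother is the treatment, so any enrolled siblings can be split and the arms pulled together

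*Combined protocol and SAP*

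**What the plan says.** **Enrolment (Material and methods).** "We enrolled all preterm neonates of gestation age 28 to 34 weeks who were admitted to NICU during the study period", after consent and subject to haemodynamic stability, established gavage feeding and limited respiratory support. The exclusions begin with "all those neonates having major anomalies incompatible with life, major malformations, syndromic babies, cleft lip and palate, genetic disorders" and go on to clinical instability and adverse events. Multiple birth is not among them, nor among the reasons for exclusion in Results.

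**Allocation.** "Gestation age-based stratification was done using 3 blocks design of 28 to 30, 30+1 to 32 & 32+1 to 34". Within these strata the unit is the infant: "Random allocation of neonates into the intervention or control groups by stratum using lottery method". Siblings are not mentioned.

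**Treatment (Procedure of intervention; Arms and intervention).** In the experimental arm the mother is trained in stages, ending with "D3: Mother performing all steps independently". For the control arm: "All steps were same as intervention group and was performed by trained staff nurses". Mothers already take part in feeding before the intervention: "All mothers in this study was involved in gavage feeding before involvement in the procedure".

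**Analysis (Statistical analysis).** Comparisons are unadjusted. Continuous variables are compared by the Mann-Whitney test, and for the others "Fisher exact/Chi square test was used to compare categorical variables". No term links infants of the same mother.

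**Data (Baseline measures; Table 1).** Multiple birth is neither a listed baseline measure nor a row of Table 1.

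**The concern.** The planned difference between the arms is who performs the stimulation. Siblings share a gestational age, so they normally fall in the same stratum, and drawing them one at a time can put them in opposite arms. The mother is then trained for one infant, while the other is supposed to be stimulated by nurses only. She has the skill and is present at feeds, and nothing in the plan tells her not to stimulate the second infant.

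The direction of the resulting bias matters. In a superiority trial, contamination of the control arm works against the sponsor's hypothesis. Here the hypotheses are of sameness (same start of oral feeding, same amount, equal efficiency), and Results reads the absence of significant differences as comparable feeding skills. Anything that makes the arms more alike therefore favours the trial's own conclusion.

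**Working it through.** **Inputs from the documents.** 130 infants were randomised (65 per arm); 107 received stimulation; 97 were analysed (49 mother arm, 48 nurse arm). Allocation is by infant, in three gestational-age strata, with block size not stated. The plan has no figure for multiples to reproduce. Its only planning figure, a sample size of 46, contains no allowance for siblings, and this point does not depend on it.

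**Assumed inputs.** *t*, the share of analysed infants who belong to an enrolled twin pair, and *ICC*, the within-pair correlation of the outcome. Neither is in the documents, so ranges are used.

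**1. Chance of a split.** Under independent 1:1 allocation each pair is split with probability 1/2. The chance of at least one split among *k* pairs is 1 − 0.5^k: 87.5% for k = 3 and 96.9% for k = 5. If short permuted blocks were used, siblings drawn consecutively would be split more often than half the time.

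**2. Controls exposed.** The share of controls with a sibling in the mother arm is t/2.

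| t | control infants who are twins (t × 48) | of these, sibling in mother arm (half) | share of controls |
|---|---|---|---|
| 0.10 | 4.8 | 2.4 | 5% |
| 0.20 | 9.6 | 4.8 | 10% |
| 0.30 | 14.4 | 7.2 | 15% |

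**3. Dilution.** If each such control were in effect treated by the mother instead of the nurse, the observed contrast would be the true contrast × (1 − t/2). For an illustrative true difference of 0.60 SD this gives 0.60 × 0.90 = 0.54 at t = 0.20 and 0.60 × 0.85 = 0.51 at t = 0.30. A simulation with 96 infants (3,000 runs per case) gave the same values, 0.54 and 0.51.

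**4. Type I error as the trial was allocated.** With *n* infants per arm and outcome variance σ², a same-arm pair adds 2·ICC·σ²/n² to the variance of the difference in means, and a split pair subtracts the same amount. When half of the pairs are split, the two cancel on average. In simulation (96 infants, 6,000 runs per case, t = 0.2-0.4, ICC = 0.5-0.8) the ordinary Mann-Whitney test at the 5% level rejected a true null in 4.7-5.3% of runs.

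**5. Type I error if siblings were kept together but still analysed as independent.** The cancellation is lost and the variance factor becomes 1 + t × ICC. For t = 0.2-0.4 and ICC = 0.5-0.8 this is 1.10 to 1.32, and the simulated type I error was 6.1-8.0%. Co-allocation therefore needs a clustered analysis with it.

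**The case against.** The strongest reply is that nothing shows the problem occurred. The documents do not say that any multiples were enrolled, and no passage reports a mother stimulating a control infant. Controls had nurse-delivered sessions at set times. Dilution by the full t/2 requires the mother to replace the nurse for every exposed control. Extra maternal sessions on top of the nurse's would be a different bias, not necessarily dilution. Some siblings may also be among the 33 of 130 randomised infants who were not analysed. All of this stands, and it makes the figures conditional upper values. It does not remove the gap in the allocation rule.

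It can also be said that the reported result would hardly move. Median time to full oral feeding was 10 against 9 days (p = 0.531 in Table 3). Undoing 15% dilution gives 1/0.85, about 1.2 days. This is fair as a rough scaling, but the documents state no equivalence margin against which to call either figure negligible.

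Two stronger readings are tempting.

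- *A reader might infer that ignoring siblings makes the standard errors too small*, for example by putting t = 0.10-0.30 and ICC = 0.3-0.8 into 1 + t × ICC and reading 1.03-1.24 as a 3-24% understatement of variance. That places every multiple with its sibling in the same arm, whereas single allocation splits about half of the pairs and the effects cancel. Standard errors that were too small would also favour finding a difference, and no tested comparison in Table 3 has p below 0.05.
- *A reader might infer from Table 1 that mothers of multiples were counted more than once*, because gravidity (20+22+7 and 26+15+7) and education (2+11+15+21 and 2+10+20+16) add to 49 and 48. These totals fit one infant per mother equally well and are no evidence that multiples were enrolled.

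**Conclusion.** The concern holds as a gap in the design with a conditional effect. The allocation rule permits siblings to be split, the mother is the experimental treatment, and the plan has no sibling rule or mother identifier. If 10-30% of infants were twins with both siblings analysed, and allocation was independent 1:1, about 5-15% of controls would have a sibling in the mother arm. The contrast would be diluted by at most that share, towards the result the trial hypothesises. If no multiples were enrolled the effect is nil. The documents do not establish that contamination happened, and they do not support a claim that the reported tests have a materially inflated type I error. It is certain that the rule is missing; the size of the effect cannot be known without a count of sibling sets.

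**What to change.** **For the completed data.**

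- Add a mother identifier, and report the number of mothers, sibling sets and split sets. If there were no multiples, one sentence to that effect closes the point.
- Otherwise, add a sensitivity analysis of the primary comparison that excludes split sets and accounts for clustering by mother in the rest, using GEE or cluster-robust errors.
- Tabulate maternal characteristics once per mother.

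**For the design.** Allocate siblings as one unit, so that the first sibling's allocation applies to all. State in the same place that the analysis is clustered by mother. The two changes belong together, for the reason in step 5 of the working.

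**Cost.** The data need one extra variable. Mann-Whitney and Fisher tests have no clustering option, so a regression-type analysis must be added alongside them. Arms within strata become slightly less even. Co-allocation also costs some effective sample size: 97/(1 + t × ICC) is 97/1.03 = 94 at t = 0.10, ICC = 0.3, and 97/1.24 = 78 at t = 0.30, ICC = 0.8. The loss is small unless both values are high.
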